19.2.2 Assessment of Relationship to Use of the Investigational Device or Procedure

The relationship between the use of the medical device (including the medical - surgical procedure) or control procedure the occurrence of each unanticipated adverse event shall be assessed and categorized. During causality assessment, clinical judgment shall be used, and the Clinical Protocol shall be consulted, as all the foreseeable adverse events and the potential risks are listed and assessed there. The presence of confounding factors, such as concomitant medication/treatment, the natural history of the underlying disease, other concurrent illness or risk factors shall also be considered.

19.2.3 SAE RELATIONSHIP ASSESSMENT

Per MDCG 2020-10/1 (May 2020), Investigators will assess the potential relationship of the SAE to the use of the investigational device (including the surgical procedure) or control procedure and classify the causality of the event according to the following definitions.

- **Not Related**: Relationship to the device or procedures can be excluded when:
 - the event has no temporal relationship with the use of the investigational device, or the procedures related to application of the investigational device;
 - the serious event does not follow a known response pattern to the medical device (if the response pattern is previously known) and is biologically implausible;
 - the discontinuation of medical device application or the reduction of the level of activation/exposure - when clinically feasible - and reintroduction of its use (or increase of the level of activation/exposure), do not impact on the serious adverse event;
 - the event involves a body-site or an organ that cannot be affected by the device or procedure;
 - the serious event can be attributed to another cause (e.g., an underlying or concurrent illness/ clinical condition, an effect of another device, drug, treatment, or other risk factors);
 - the event does not depend on a false result given by the investigational device used for diagnosis, when applicable;
 - harms to the subject are not clearly due to use error;
 - In order to establish the non-relatedness, not all the criteria listed above might be met at the same time, depending on the type of device/procedures and the serious adverse event.
- **Possible:** The relationship with the use of the investigational device or the relationship with the procedure is weak but cannot be ruled out completely. Alternative causes are also possible (e.g., an underlying or concurrent illness/ clinical condition or/and an effect of another device, drug, or treatment). Cases where relatedness cannot be assessed or no information has been obtained should also be classified as possible.
- **Probable**: The relationship with the use of the investigational device or the relationship with the procedure, seems relevant and/or the event cannot reasonably be explained by another cause.
- **Causal Relationship**: The serious adverse event is associated with the investigational device or with procedures beyond reasonable doubt when:
 - the event is a known side effect of the product category the device belongs to or of similar devices and procedures;
 - the event has a temporal relationship with investigational device use/application or procedures;
 - the event involves a body-site or organ that
 - the investigational device or procedures are applied to;
 - the investigational device or procedures have an effect on;
 - the serious event follows a known response pattern to the medical device (if the response pattern is previously known);

- the discontinuation of medical device application (or reduction of the level of activation/exposure) and reintroduction of its use (or increase of the level of activation/exposure), impact on the serious event (when clinically feasible);
- other possible causes (e.g., an underlying or concurrent illness/ clinical condition or/and an effect of another device, drug, or treatment) have been adequately ruled out;
- harm to the subject is due to error in use;
- the event depends on a false result given by the investigational device used for diagnosis, when applicable;
- In order to establish the relatedness, not all the criteria listed above might be met at the same time, depending on the type of device/procedures and the serious event.

Where the Investigator or Sponsor remains uncertain about classifying the event, it should not exclude the relatedness and the Investigator should classify the event as "Possibly Related".

19.2.4 SAE REPORTING

Flow Neuroscience AB is responsible for the classification and reporting of adverse events and ongoing safety evaluation of the clinical investigation in line with ISO 14155:2020 and US/UK regulatory requirements.

Investigator will report "to the Sponsor, without unjustified delay, all serious adverse events and device deficiencies that could have led to a serious adverse device effect; this information shall be promptly followed by detailed written reports" [ISO 14155:2020 § 9.8 b]. Device malfunctions and use errors should also be reported without unjustified delay.

In the event of becoming aware of any SAE (including all device deficiencies), anticipated or unanticipated, the Investigator will report the event to Flow Neuroscience AB and Curebase immediately (at least within 24 hours after first knowledge of the event) by entering SAE information in the EDC. In the event the EDC is unavailable for any reason, notification to Flow Neuroscience AB should be made via email as follows:

Sponsor Contact: [name] E-mail: [contact] [contact]

The Investigator should provide additional information on the SAE by updating the information in the EDC as updates become available. Flow Neuroscience AB may also ask for additional clinical reports including redacted source documents to be provided by the Investigator to assist in the assessment of the event. Significant new information and updates should continue to be submitted promptly to and entered in the EDC as they become available, and the Investigator should follow the SAE until it is resolved, or no further improvement is expected.

It is the responsibility of each Investigator to report all SAEs and/or SADEs to the IRB/EC, according to national regulations and IRB/EC requirements. A copy of the IRB/EC report should be

CONFIDENTIAL Page **54** of **69**

forwarded to Flow Neuroscience AB. In countries that require the Sponsor to report safety events rather than investigators, the Sponsor (Flow Neuroscience AB) will report SAEs and/or SADEs to the EC.

Flow Neuroscience AB will ensure that all SAEs and device deficiencies that could have led to a SAE are reported to the Competent Authorities in accordance with European Medical Devices directives and all applicable national regulations.

Flow Neuroscience AB will ensure that all events that meet the vigilance requirements as described in MDCG 2020-10/1 (Safety reporting in clinical investigations of medical devices under the Regulation (EU) 2017/745) are reported to the Competent Authorities in accordance with European Medical Devices directives and all applicable national regulations.

19.2.5 DETERMINATION AND REPORTING OF UNANTICIPATED ADVERSE DEVICE EFFECTS (US SITES)

The Sponsor shall review all reported SAEs to evaluate whether they meet the criteria for an Unanticipated Adverse Device Effect. For adverse events that are determined to be UADEs, the Sponsor will submit an expedited safety report to the FDA's Center for Devices and Radiological Health (CDRH). The expedited safety report will be submitted to the FDA as soon as possible and, in no event, later than ten (10) business days after the Sponsor first receives notice of the UADE. A copy of this safety report will be provided to all participating study Investigators.

If, following receipt and investigation of follow-up information regarding an adverse event that was previously determined not to be a UADE, the Sponsor determines that the event does meet the requirements for expedited reporting, the Sponsor will submit a report as soon as possible, but in no event later than **ten (10) business days** after this is determined.

19.3 TREATMENT OF AEs

The Investigator will treat all participants who experience an adverse event directly related to the device.

19.4 SAFETY OVERSIGHT: CLINICAL EVENTS COMMITTEE (CEC)

The Clinical Events Committee (CEC) will adjudicate all AEs and protocol deviations. SAEs and AEs deemed "definitely," "probably," and "possibly related" or with an "unknown relationship" to the device or procedure, primary endpoint failure, and the following neurological AEs, including neurologic deterioration will be reviewed.

19.5 SAFETY/SUICIDE RISK MANAGEMENT PLAN

All study participants will be provided a safety crisis action plan for suicide risk at the time of study enrollment. The crisis action plan will include the following information;

- Name, address, and telephone number of the closest hospital emergency department near the study participant's residence
- Contact details of next of kin/friends for support
- Study participant's regular treating physician's name and contact information

- National Suicide Prevention Lifeline [contact]
- Strategies for coping with suicidal ideation/crisis.
- Further, subjects will be notified that study personnel will contact their psychiatrist in the case of worsening depression/suicidality (worsening depression is defined as 30% increase in HDRS-17 score compared to baseline).

All participants will be informed about the warning signs of suicidal ideation and behavior at the start of the study. Throughout the study, subjects will be monitored by study psychiatrists.

If the C-SSRS questions 4, 5, and 6b are positive during the study assessments, the participant will be asked to go to the nearest emergency department or mental health crisis center.

The suicide risk management plan document (attachment "Brown_StanleySafetyPlan") will be completed with patients.

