12.3 EXCLUSION CRITERIA

Participants who meet any of the following criteria will be excluded from participating in this study:

- 1. Are in a current state of mania, as determined by the YMRS or psychosis, as determined by the MINI.
- 2. Are diagnosed with vitamin or hormonal deficiencies that may mimic mood disorders, as determined by the investigator.
- 3. Are currently receiving any other interventional therapy for MDD other than a stable regimen of antidepressants or psychotherapy as defined in the inclusion criteria.
- 4. Considered to have treatment resistant depression as defined by inadequate clinical response to 2 or more trials of antidepressants at an adequate dose and duration.
- 5. Have a history of electroconvulsive therapy (ECT), transcranial magnetic stimulation (TMS), cranial electrotherapy stimulation (CES), transcranial direct current stimulation (tDCS), deep brain stimulation (DBS), or other brain stimulation.
- 6. Patient answers Yes to Questions 4, 5 or 6 on the Columbia Suicide Severity Rating Scale (C-SSRS) Triage and Risk Identification Screener.
- 7. Any previous hospitilization for suicidal behavior.
- 8. Have chronic severe insomnia (< 4 hours of sleep each night), or depression secondary to chronic insomnia or sleep apnea
- 9. Have any structural lesion (e.g., any structural neurological condition, or more subcortical lesions than would be expected for age or have had a stroke that affects stimulated area or connected areas) or any other clinically significant abnormality that might affect safety, study participation, or confound interpretation of study results, as determined by the investigator.
- 10. Have any implant in the brain (e.g., DBS) or neurocranium, or any other active implantable medical device.
- 11. Have any neurocranial defect.
- 12. Have a history of epilepsy or seizures (including history of withdrawal / provoked seizures).
- 13. Have shrapnel or any ferromagnetic material in the head.
- 14. Have any disorder that would impair the ability to complete the study questionnaires.
- 15. Have been diagnosed with autism spectrum disorder.
- 16. Are actively abusing substances (<1 week prior to enrollment).
- 17. Have a cognitive impairment (including dementia).
- 18. Have a history of mania or psychosis.
- 19. Are currently using any medications that affect cortical excitability (e.g., benzodiazepines, epileptics, etc.).
- 20. Are currently experiencing symptoms of withdrawal from alcohol or benzodiazepines.

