- 21. Have been diagnosed with Parkinsonism or other movement disorder as determined by the investigator to interfere with treatment.
- 22. Have ever taken esketamine / ketamine for treatment of depression.
- 23. Have ever been admitted to hospital for depression.
- 24. Have ever been diagnosed with obsessive-compulsive disorder (OCD) or bipolar type 1 or 2 disorder.
- 25. Is diagnosed with an active primary anxiety disorder, or PTSD, agoraphobia, anorexia or bulimia, panic or personality disorder with active symptoms.
- 26. Have a history of psychosurgery for depression.
- 27. Have any history of myocardial infarction, coronary artery bypass graft (CABG), coronary heart failure (CHF), or history of other cardiac issues.
- 28. Are currently experiencing or have a history of intractable migraines.
- 29. Are a chronic tobacco smoker, as defined by smoking by smoking >100 cigarettes (including hand-rolled cigarettes, cigars, cigarillos, etc.) in their life-time and have smoked every day for the last 7 days.

- 30. If female and of child-bearing potential, currently pregnant or breastfeeding or planning to become pregnant or breastfeed any time during the study.
- 31. Are currently a prisoner.
- 32. Are participating concurrently in another clinical investigation or have participated in a clinical investigation within the last 90 days or intend to Participate in another clinical investigation during the study, and where the participation in the other investigation might interfere with the results of this trial as deemed by the PI.
- 33. Have any medical condition or other circumstances, in the judgment of the investigator, that might interfere with the ability to complete follow-up visits and the self-reported MADRS-s in the app.
- 34. Have any condition which, in the judgment of the Investigator, would preclude adequate evaluation of the device's safety and performance.
- 35. A Subject who meets any of the exclusion criteria during study participation will be discontinued from the study

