15.2 TREATMENT FAILURES

The following situations will be considered treatment failures and participants will be withdrawn from the trial:

- 30% increase in HDRS-17 score compared to baseline.
- Suicidal attempts / completion
- Device related SAE
- 15.3 LOST TO FOLLOW-UP (LTFU)

Participants who miss the final, 10-week study visit will be regarded as Lost to Follow-Up. As described in the Statistical Analysis Plan, these subjects will be included in the primary analysis through Multiple Imputation. Therefore, this definition of LTF only applies to study operations and not data analysis. Curebase or site staff should perform and document a minimum of three attempts to contact them via phone to complete the final study visit prior to considering the participant LTFU. The Curebase or site staff should document the date and type of attempted communication.

All efforts should be made to have participants complete all follow-up visits.

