15.4 WITHDRAWALS

Participants have the right to withdraw from the clinical investigation at any time and for any reason. The Principal Investigator will ask the reason for their withdrawal and will record all information regarding the participant discontinuation.

A Participant may be withdrawn from the clinical investigation for the following reasons:

- Participants may choose to withdraw from the clinical investigation under the terms of the Declaration of Helsinki and their consent documentation without having to give a reason;
- Any unanticipated adverse event which, in the opinion of the Principal Investigator, is related to the treatment and will endanger the well-being of the participant if treatment is continued;
- Development of any intercurrent illness(es), infection or condition(s) that might interfere with the clinical investigation;
- Non-compliance with the clinical investigation procedures deemed by the Principal Investigator to be sufficient to cause discontinuation;
- Any problem deemed by the Investigator to be sufficient to cause discontinuation.

Participants will be withdrawn from the trial if they do not comply with the intervention, namely if they are unable to have a minimum of 60% of the tDCS session (22 (660 minutes) out of 36 sessions at week 10) during the blinded phase, or if they develop serious adverse effects from any part of the study. Recording of the reasons for withdrawal will be made. Their GP will be informed about their withdrawal, and they will have a telephone follow up at 1 month following their withdrawal.

If a participant is withdrawn, their device is disabled to make sure they cannot continue the treatment.

Regardless of the reason for withdrawal, data available for the participant at the time of withdrawal, including the reason for withdrawal, will be entered on the Case Report Forms. The research staff will request to have an optional early termination visit to collect the same data as at the week 10 and week 20 interview. The Principal Investigator will treat all participants discontinued from the investigation due to an unanticipated adverse event, directly related to the investigation, until the reaction resolves. A participant that has been withdrawn from the study after treatment start will not be replaced.

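### The in-study C-SSRS trigger for emergency referral (Section 19.5) does not match the C-SSRS trigger for exclusion and discontinuation (Section 12.3, items 6 and 35), and the protocol does not say that the difference is intended

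*Protocol*

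**What the plan says.** Three places in the protocol set the relevant rules, and a fourth sets a consequence.

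- **Section 12.3, item 6 (repeated in the Section 6 synopsis).** A person is excluded if "Patient answers Yes to Questions 4, 5 or 6 on the Columbia Suicide Severity Rating Scale (C-SSRS) Triage and Risk Identification Screener". One positive item is enough, and the form is named.
- **Section 12.3, item 35 (also in the synopsis).** "A Subject who meets any of the exclusion criteria during study participation will be discontinued from the study". Item 6 therefore also operates as a discontinuation rule during the study, by reference.
- **Section 19.5.** The in-study referral rule applies "If the C-SSRS questions 4, 5, and 6b are positive during the study assessments"; in that case "the participant will be asked to go to the nearest emergency department or mental health crisis center". The form is not named.
- **Section 15.4.** "If a participant is withdrawn, their device is disabled to make sure they cannot continue the treatment".

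The protocol neither defines item 6b nor uses it anywhere else. The visit lists in Sections 13.1 to 13.8 and the instrument description in Section 14 refer only to the C-SSRS, without a version.

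**The concern.** The same questionnaire answers feed two mandatory in-study rules, and the rules are worded differently in two respects: 'or' against 'and', and item 6 against item 6b. Staff conducting a remote visit have to act on the answers during the call. If they follow Section 19.5 as written, the referral instruction can fail to fire for an answer that Section 12.3 treats as serious enough to end participation. That participant would leave the study, and lose the device, with no instruction in Section 19.5 that applies to the answer given.

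What is at stake is participant safety and uniform handling of the same answers. It is not the primary analysis.

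**Working it through.** No planned figure is involved, so there is none to reproduce. The check sets the rules side by side and counts the yes/no answer patterns on which they disagree.

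**Inputs**

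| Rule | Source | Items | Connective | Form named | Action |
|---|---|---|---|---|---|
| Discontinuation | 12.3 items 6 and 35; 15.4 | 4, 5, 6 | or | Triage and Risk Identification Screener | Discontinue; device disabled |
| Referral | 19.5 | 4, 5, 6b | and | none | Asked to attend emergency or crisis care |

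I take discontinuation under item 35 to be withdrawal in the sense of Section 15.4, since that section stands under the chapter on early discontinuation of participants.

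**Case A: 6b is another label for item 6, and 'and' means all.**
- Patterns: 2 × 2 × 2 = 8.
- Discontinuation rule fires unless all three items are negative: 8 − 1 = 7.
- Referral rule fires only if all three are positive: 1.
- Discontinued without referral: 7 − 1 = 6 of 8. Item 4 alone positive is one of them.

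**Case B: 6b is a sub-part of item 6, and 'and' means all.**
- Item 6 has three states: negative, positive without 6b, and positive with 6b. Patterns: 2 × 2 × 3 = 12.
- Discontinuation fires in 12 − 1 = 11; referral in 1.
- Discontinued without referral: 11 − 1 = 10 of 12.

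**Case C: 6b is a sub-part of item 6, and 'and' is a list (any of 4, 5, 6b).**
- Referral fails to fire only when 4, 5 and 6b are all negative, which is 2 patterns (item 6 negative, or item 6 positive without 6b). It fires in 12 − 2 = 10.
- Discontinued without referral: 11 − 10 = 1 of 12, namely item 6 positive with 4, 5 and 6b negative.

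**Case D: 6b is another label for item 6, and 'and' is a list.**
- Both rules fire in the same 7 of 8 patterns. There is no mismatch.

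The rules agree only in Case D, which needs two assumptions that the protocol does not state. The counts give the logical extent of the mismatch. They weight every pattern equally and are not estimates of how many participants would be affected.

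**The case against.** The strongest reply is that entry, discontinuation and emergency referral are separate decisions and may have separate thresholds. For a participant positive on item 4 alone, staff can obey every passage: discontinue under item 35, and do not apply the referral instruction. No passage forbids what another requires. This stands, so a reader who infers an outright contradiction goes too far. What remains is that nothing in the protocol says the difference is intended. Section 19.5 does not mention discontinuation, and item 35 does not mention referral.

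A second reply is that 'and' in Section 19.5 simply lists the questions that matter. This is a natural reading and removes most of the mismatch (Case C) or all of it (Case D). But the text does not say so, exclusion 6 shows that the authors write 'or' when one item suffices, and the meaning of 6b cannot be settled from the document.

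Third, there are safeguards. The graduate researchers are supervised by a psychiatrist (Section 7), study psychiatrists monitor participants, every participant has a crisis action plan, and study staff contact the participant's psychiatrist if depression or suicidality worsens (Section 19.5). The attached safety plan, which is not shown, may hold further detail. These reduce the practical risk, but they do not settle which answers trigger the referral instruction.

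Three stronger inferences are not supported:

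- **A conflict with Section 15.2.** That section lists "Suicidal attempts / completion" as a treatment failure and does not mention C-SSRS answers. It is not an exhaustive list of withdrawal reasons: Section 15.4 adds others, including investigator judgement, and item 35 adds more. Its silence contradicts nothing.
- **More missing Week 10 data.** Section 19.5 governs referral, not withdrawal. Misreading its 'and' does not change who is withdrawn, because item 35 acts through the clear 'or' in exclusion 6.
- **Exposure counted as every scheduled C-SSRS for all 270 randomized subjects.** Week 20 applies only to those who enter the open-label phase (Section 13.9), and the protocol gives no rate of single positive items.

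**Conclusion.** The point holds as a wording inconsistency in a safety rule. Section 19.5 and exclusion criteria 6 and 35 attach different C-SSRS triggers to two in-study actions. They do so without stating that the difference is deliberate, without defining 6b and without naming the form used during the study. Read literally, a single positive item leads to discontinuation and a disabled device but does not meet the referral trigger.

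The logical size depends on the reading: 6 of 8 patterns if 6b is item 6, 10 of 12 if 6b is part of item 6, 1 of 12 if in addition the 'and' is a list, and none if the 'and' is a list and 6b is item 6. The number of participants affected cannot be derived from the protocol. Type I error, power and sample size are untouched. The point is still worth correcting, because a safety instruction followed as written can fail to fire for an answer that the same protocol treats as disqualifying.

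**What to change.** Reconcile Section 19.5 with Section 12.3, items 6 and 35. State:

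1. which C-SSRS version is used at in-study assessments;
2. which items count, with 6b either defined or replaced by the label used on that form;
3. whether any one item or all of them are needed;
4. which action or actions each trigger leads to.

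If referral and discontinuation are meant to have different thresholds, one sentence saying so would suffice in place of alignment, provided that the items and the connective are clear. Repeat any change in the Section 6 synopsis. Which answers should lead to which action is for the sponsor and investigators to decide.

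The cost is a wording amendment and a short retraining note for the staff who administer the scale. No analysis, sample size or visit schedule changes.
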